9 TRAINING

9.1 INVESTIGATORS DEVICE TRAINING

[Redacted text block]

[Redacted text block]

9.2 TRAINING OF INVESTIGATIONAL CENTER PERSONNEL

[Redacted text block]

9.3 TRAINING DOCUMENTATION

10 INVESTIGATIONAL DEVICE MANAGEMENT

10.1 DEVICE SHIPMENTS

Devices will be transported to the study center when the Clinical Study Agreement is in place, the study center has obtained applicable regulatory (e.g., EC, Health Canada, MOH) approvals, and a subject eligible for implant has been identified.

Devices will be provided to the study center as needed for scheduled implant procedures. All investigational devices used in this study for investigational purposes will be labeled with regional appropriate clinical investigation labeling and warnings.

10.2 DEVICE ACCOUNTABILITY

All device shipments will have inventory and shipment records. Devices may be hand carried to participating study centers by Study Sponsor personnel and will be accompanied by delivery of investigational device documentation (packing lists, transfer of investigational product form, etc.). The Investigator(s) or designee will take inventory of the product and complete the delivery documentation with receipt date and signature. Both the study center and the Study Sponsor will retain copies of these documents. The Investigator will maintain a Device Accountability Log (as provided by the Sponsor) of all investigational devices documenting their receipt, disposition and return during this clinical study. The log will be kept with the documents for the clinical study and will be available for review during Study Sponsor monitoring visits.

Upon Sponsor request or when enrollment has ended, FORMA System components must be returned to Edwards Lifesciences and the date of return must be recorded on the log.

10.3 DEVICE STORAGE

The device inventory will be stored in a locked, controlled, cool and dry area as described in the Instructions for Use (IFU) and/or presented on the device labeling. This secured area will be only accessible to the Investigators or approved designee. Only investigators trained and identified in the Delegation of Authority form on file at Edwards Lifesciences may use the investigational devices.

10.4 DEVICE RETURN

The Investigator will be notified in writing upon termination of the clinical study. All unused devices in original package and/or those in opened packages as well as those removed from the original package will be returned upon receipt of this notice. The Investigator will receive instructions from the Study Sponsor on the return process. The Investigator's copy of the Device Accountability log must document any unused devices that have been returned.

Used devices may be handled and disposed of in the same manner as hospital waste and bio-hazardous materials in accordance with local regulations. There are no special risks related to the disposal of these devices. Devices that malfunction or are related to a serious adverse event or device effects will be returned to the Study Sponsor for further investigation (when possible). All returns and dispositions of devices will be captured on the Device Accountability Log Procedure needed.

11 DATA COLLECTION AND REPORTING

11.1 DATA COLLECTION METHODS

The Study Sponsor will provide the study center with the clinical protocol, electronic case report forms, sample informed consent form, and all other necessary study-related documents. Study Sponsor's Clinical Affairs Department, or designee, will conduct all aspects of data quality control and assurance of the study center including but not limited to, data reviewing, data monitoring, and form collection.

11.2 CASE REPORT FORMS

Electronic CRFs will be used to collect all patient data during the trial. Paper copies will be available for printing on the website. An e-mail notification will be sent to Edwards Lifesciences when enrollment data is collected into the website. Electronic CRFs must be fully completed for each patient, and signed electronically by the investigator and/or designee. If for any reason the eCRFs are unavailable, or access to the electronic database is limited, paper CRF forms must be completed and submitted to study manager. The eCRFs should be completed at the first earliest opportunity.

The investigator, or an individual designated by him/her, is responsible for recording all data from the trial onto the eCRFs on a dedicated website. All data entered is subjected to data type verification and range checking. The operator is notified of errors that may occur, and depending on the data verification sub-routines, the operator might need to resolve that error before moving to the next entry field. The investigator is required to provide an electronic signature on the appropriate eCRF pages to verify that he/she has reviewed the recorded data.

Completed eCRFs will be reviewed at the investigational site and remotely by authorized Edwards Lifesciences personnel at regular intervals throughout the trial. Each data record is evaluated with extensive electronic intra-form and inter-form edit checking at regular intervals. If an error is discovered, the clinical site research Study Coordinator will be notified. Corrections to the eCRFs will be made by the research Study Coordinator, approved by the investigator or designee and verified by the sponsor.

Data submission will be monitored closely. Sites that do not complete all data entry tasks in a timely manner may be prohibited from enrollment until data submission is current.

The cycle of data editing will be ongoing until all the data are clean. The sponsor or designee will monitor the clinical site for source documentation verification. If further data entry or source documentation errors are discovered during the site visit, additional queries will be generated and will have to be addressed by the clinical site.

11.3 SOURCE DOCUMENTATION REQUIREMENTS

The Clinical Research Coordinator (CRC) designated by the Investigator, and documented on the Delegation of Authority log, will perform primary data collection drawn from source documentation review (subject's medical record). All data that is entered in the eCRFs must have source documentation available in the subject medical records. Data to be collected for the study purposes must not be entered directly onto eCRFs. Protocol deviation information can be recorded directly on the protocol deviation eCRF. The data must be recorded from original source documents and available for review by the study monitor. Regulations require that Investigators maintain information in the study subject's medical records that corroborate data collected on the eCRFs. The source documentation may consist of but is not limited to: operative or procedure reports, progress notes, discharge summaries, laboratory reports, radiographic reports, medication logs, and worksheets. Source Documents may be in electronic form and/or hard (paper) copies.

11.4 QUALITY CONTROL AND QUALITY ASSURANCE PROCEDURES

Because of the potential for errors and inaccuracies in entering data into eCRFs, originals or photocopies of all relevant procedural records and reports, post-procedural examinations, laboratory and other test results may be kept on file in the Investigator's subject study files. Access to eCRFs and copies of test results must be available at all times for inspection by the study monitor.

All clinical sites will be audited periodically by a study monitor employed by Edwards for protocol adherence, accuracy of eCRFs, and compliance to applicable regulations. Evident patterns of non-compliance with respect to these standards will be cause for the site to be put on probation for a period of one month. If corrective actions are not subsequently undertaken, the clinical site will be asked to withdraw.

Operational data is hosted for full security and availability internally by Edwards. Edwards data management provides the highest standards of availability and security:

- Hosting facility is a multi-level protected environment.
- Access is severely restricted with high-end user recognition technology.
- Multi-points backup of critical data is standard.
- Firewalls and other undisclosed technologies provide strong data security.
- Availability all year-round 24 hours a day.

Passwords will be issued to appropriate data management personnel to ensure confidentiality and protection of the data by allowing variable levels of access to the computer system.

12 REPORTABLE EVENTS / EFFECTS

12.1 REPORTING PROCEDURE

Study subjects will be carefully monitored during the clinical study for any possible adverse event. All adverse events will be fully investigated by the Investigator. Appropriate treatment for the subject will be initiated while the study follow-up continues. Adverse events will be followed until they are adequately resolved or explained.

The Investigator will attempt to assess the involvement of the investigational device and / or study procedure in the adverse event according to five different levels of causality (See Section 19, Definitions, for causality definitions). All observations and clinical findings, including the nature or the severity, will be documented on the appropriate case report form.

The Investigator will report any serious adverse event, anticipated or unanticipated, to the Study Sponsor within 24 hours after first knowledge of the event. Notification to the Study Sponsor will be made as follows:

In addition, the Investigator will report all adverse events to their Ethics Committee Institutional Review Board in accordance with their requirements. Adverse events will be reported to the National Regulatory Agency in accordance with the applicable requirements, for example as described in the “SAE Documentation, Evaluation and Reporting Procedure to the Competent Authorities” document for Germany.

12.2 DEFINITIONS

12.2.1 ADVERSE EVENT

An adverse event (AE) is defined in ISO 14155:2011 as any untoward medical occurrence, unintended disease or injury, or untoward clinical signs (including abnormal laboratory finding) in subjects, users or other persons, whether or not related to the investigational medical device.

Note: anticipated adverse events are adverse events that have been identified as possible adverse events related to the investigational medical device or the study procedure. The anticipated events of this clinical study are outlined in Section 3.1, Potential Risks

12.2.2 ADVERSE DEVICE EFFECT

An adverse device effect (ADE) is defined in ISO 14155:2011 as any adverse event related to the use of an investigational medical device. This definition includes:

- Adverse event resulting from insufficient or inadequate instructions for use, deployment, implantation, installation, or operation, or any malfunction of the investigational medical device.
- Any event resulting from use error or from intentional abnormal use of the investigational medical device.

12.2.3 SERIOUS ADVERSE EVENT

A serious adverse event (SAE) is defined in ISO 14155:2011 as an adverse event that:

1. led to death
2. led to serious deterioration in the health of the subject that either resulted in:
 - a. a life-threatening illness or injury, or
 - b. a permanent impairment of a body structure or a body function, or
 - c. in-patient or prolonged hospitalization, or
 - d. medical or surgical intervention to prevent life threatening illness or injury or permanent impairment to a body structure or a body function.
3. led to fetal distress, fetal death or a congenital abnormality or birth defect (not anticipated in this study as pregnant women are excluded from the study).

12.2.4 SERIOUS ADVERSE DEVICE EFFECT

A serious adverse device effect (SADE) is defined in ISO 14155:2011 as an adverse device effect that resulted in any of the consequences characteristics of a serious adverse event or that might have led to any of these consequences if suitable action had not been taken or intervention had not been made or if circumstances had been less opportune.

12.2.5 UNANTICIPATED SERIOUS ADVERSE DEVICE EFFECT

Unanticipated adverse device effect (USADE) is defined in ISO 14155:2011 as any serious adverse device effect which by its nature, incidence, severity or outcome has not been identified in the risk analysis section of the study protocol.

12.2.6 DEVICE DEFICIENCY AND MALFUNCTION

Device deficiency is defined in ISO 14155:2011 as an inadequacy of a medical device with respects to its identity, quality, durability, reliability, safety or performance.

Device deficiencies include malfunctions, use errors and inadequacy in the information supplied by the manufacturer.

Device malfunction is defined in ISO 14155:2011 as a failure of an investigational medical device to perform in accordance with its intended purpose when used in accordance with the Instructions for Use.

Device embolization is defined in ISO 5840-3 as dislodgement from the intended and documented original position to an unintended and non-therapeutic location.

Device detachment is defined as separation, under the action of applied stress or strain, of any part of the investigational device that was previously intact.

Device migration is defined in ISO 5840-3 as detectable movement or displacement of the device from its original position within the implant site, without embolization.

Structural component failure is defined as degradation of structural integrity of the support structure (e.g., railing) that results in the functional performance of the implant no longer being acceptable and/or that results in adverse events.

Device deficiencies and malfunctions will be reported to the sponsor.

12.3 DEATHS AND EXPLANTS

12.3.1 SUBJECT DEATHS

In the event of subject death, every effort should be made to obtain a copy of the autopsy report and/or death summary. Information on the cause of death and its relationship to the investigational device or study procedure will be determined by the Investigator. Copies of an autopsy report, if available, and/or a death summary are to be forwarded to the Study Sponsor.

If a device is explanted during autopsy, the device should be returned to the Study Sponsor for analysis. Return kits for devices will be provided upon request by the clinical monitor.

12.3.2 DEVICE EXPLANTS

In the event the study devices are explanted, in the intra-operative or early post-operative period a copy of the explant procedure report must be provided to the Study Sponsor. Information on the cause of explant and its relationship to the study devices will be determined by the Investigator. Explanted study devices during this period must be returned to Study Sponsor for analysis.

In the event the study device is explanted, in the late post-operative period, every effort should be made to obtain a copy of the explant procedure report, as applicable. Information on the cause of explant and its relationship to the study device will be determined by the Investigator. Copies of an explant report, if available, are to be sent to the Study Sponsor. Explanted study devices during this period should be returned to Study Sponsor for analysis. Investigational devices shall be returned to the Study Sponsor as described in Section 10.4.

13 STATISTICAL ANALYSIS

13.1 SAMPLE SIZE

The primary endpoint is all-cause mortality at 30-days. Survival probabilities and standard errors will be estimated using the Kaplan Meier method and Greenwood formula respectively.

A performance goal of 18% was pre-specified for the 30-day rate of all-cause mortality in TVR (Tricuspid Valve Regurgitation) subjects treated with the Edwards FORMA Tricuspid Transcatheter Repair System, which was based on review of literature and early clinical studies (reference Section 1.3). The hypothesis for the primary endpoint is as follows:

- $H_0: \pi \geq 18\%$
- $H_A: \pi < 18\%$

Where π represents the all-cause mortality rate at 30 days.

The study is powered to detect a clinically significant difference between the expected mortality of the treatment group and the 18% Performance Goal. Based on the initial experience of the device (with some additional uncertainty assumptions), the estimated true rate was established to be 7.5% or less. Targeting a clinically significant difference of 10.5% (absolute reduction of greater than 50%), a sample size of 63 subjects will yield

at least 80% power to detect this difference at a significant level of 0.05. With a proportion of up to 9 investigational centers utilizing a roll-in subject and with a potential dropout rate of approximately 10%, an enrollment target of 78 subjects will ensure a sample size of 63 is available for analysis.

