**Table 9 - Follow-up Visit Windows**

Scheduled Follow-up Interval	Follow-up Window
1 month (30 days)	± 7 days
6 months (183 days)	± 30 days
Annually (365 days) up to 3 years	± 45 days

During the follow-up visits, medical information, findings and results will be entered in the appropriate electronic case report forms.

Study subjects who have signed the Informed Consent, are deemed eligible and considered enrolled in the study but do not have the study procedure (incision) occur will be exited from the study immediately.

Study subjects who have signed the Informed Consent, are enrolled in the study, have the study procedure (incision) occur but do not receive the investigational device will be classified as “non-implanted” study subjects and exit the study at the 6 month follow-up visit. Non-implanted study subjects must complete safety evaluations but, will be exempt from all other study follow-up visit procedures.

Table 10 - Summary of Required Study Procedures

STUDY PROCEDURES	BASELINE	IMPLANT PROCEDURE ¹ (Day 0)	DISCHARGE ²	1 MONTH (30 ± 7 days)	6 MONTHS (183 ± 30 days)	ANNUAL (for 3 yrs) (365 ± 45 days)
Informed Consent	X					
Medical History	X					
Clinical Evaluation	X		X	X	X	X
NYHA Class Assessment	X			X	X	X
Health Status Questionnaires	X			X	X	X
Six Minute Walk Test	X			X	X	X
Safety Evaluation		X	X	X	X	X
Brain Natriuretic Peptide (BNP)	X		X	X	X	X
CBC and Platelet Count	X		X	X	X	X
Complete Metabolic Panel	X		X	X	X	X
Liver Panel	X		X	X	X	X
PTT/aPTT or PT/INR	X		X	X	X	X
βHCG	X ³					
eGFR	X ⁴		X	X	X	X
Troponins and CK-MB	X	X ⁵	X ⁶			
ECG	X		X	X	X	X
Transesophageal Echocardiogram	X ⁷	X				
Transthoracic Echocardiogram	X		X	X	X	X
Pre-Implant Computed Tomography	X					
Angiographic Imaging		X				
Invasive Hemodynamic Monitoring/Rt Heart Cath.	X ⁸	X				

¹ Implant procedure must be scheduled within 90 days of the baseline transthoracic echocardiogram and 90 days of the pre-implant procedure computed tomography (CT). If a pre-existing CT within 6 months of the scheduled implant captures all the required anatomy for necessary measurements & the anatomy has not changed, the baseline CT can be waived & is not required to be repeated.

² Discharge from hospital/unit post implant procedure

³ βHCG for women who are not sterile or post-menopausal

⁴ eGFR result of < 25 is an exclusion from study participation

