8.9 WITHDRAWAL CRITERIA AND PROCEDURES

The Investigator will make every attempt to follow the subjects at each of the required assessment periods. The reason for the withdrawal will be documented on the appropriate case report forms and in the medical records for each subject who has withdrawn.

Subjects may be withdrawn from the study for any of the following reasons:

- Subject Withdrawal

The subject may voluntarily withdraw from the clinical study at any time, without penalty or loss of benefits to which they are otherwise entitled.

- Physician Withdrawal

The Principal Investigator also has the right to withdraw a subject if they feel it is in the best interest of the subject to do so.

- Lost to Follow-up

If a subject cannot be reached for a follow-up visit, the Investigator will document the contact efforts made to the subject and/or effort to obtain hospital records in the appropriate electronic case report form. If the subject cannot be reached in any way, or misses a visit, the subject will be considered "unable to contact" for that time interval. After three (3) documented unsuccessful attempts to make contact prove unsuccessful, a certified letter will be sent to the subject's residence. If there is no response after the certified letter is sent, the subject will be considered "lost to follow-up."

In all cases of withdrawal (as described above), withdrawn subjects will not undergo further study follow-up procedures after the time of study exit. A study subject that has been withdrawn from the study will not be replaced.

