8.10 SUBJECT STUDY COMPLETION

Study subjects complete and exit the study when no additional follow-up visits, procedures, or data collection are required. Patients will then continue to be followed by their primary health care provider as required.

A subject will also be exited from the study in the following instances:

- Subject signs informed consent form, is deemed eligible and considered enrolled but does not undergo the study procedure
- Subject undergoes study procedure and does not receive investigational device (will continue in study for safety evaluations only and exit the study at the 6 month follow-up visit)
- Implanted subject requires the investigational device to be explanted for any reason (will continue in study for safety evaluations only and exit the study at the 6 month follow-up visit)
- Subject is lost-to-follow-up
- Subject withdraws participation from the study or is withdrawn from the study
- Subject expiration

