13.3 ANALYSIS POPULATION

The analysis population will be grouped into four analysis cohorts that in total comprise all subjects enrolled in this study. The analysis cohorts are defined below:

- Enrolled Cohort: all subjects enrolled in the study
- As Treated (AT) Cohort: all subjects who are enrolled and undergo the study procedure (chest incision)
- Implanted Cohort: all subjects who undergo the study procedure (chest incision), receive and retain the investigational device upon leaving the procedure room
- Roll-In Cohort: first subject enrolled and treated at a center that does not have previous device or procedure experience and is classified as a “roll-in” subject

The primary endpoint will be reported based on the AT cohort. For the secondary endpoints and clinical outcomes, technical success analysis will be performed for the AT cohort, while device success, procedure success and clinical outcomes analyses will be performed for the implanted cohort. Roll-In subjects will be analyzed separately. Subject listings for adverse events, deaths will include all enrolled subjects.

For subjects with major protocol violations, which include but are not limited to study criteria and informed consent violations, a secondary analysis will be conducted in which those subjects will be excluded from the implanted cohort analyses.

Further analysis plans will be outlined in the statistical analysis plan.

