Device Detachment	Separation, under the action of applied stress or strain, of any part of the investigational device that was previously intact.
Device Embolization	Refer to ISO 5840-3 definition
Device Malfunction	Refer to ISO 14155 definition
Device Migration	Refer to ISO 5840-3 definition
Device Success	
Device Success (at 1 month, 6-months and annually):
 
 • Alive, with • Original intended device in place, and • No additional surgical or interventional procedures related to the device, and • TR reduction (assessment made by change in EROA) compared to baseline and TV gradient $\leq 5\text{mmHg}$
Embolism	
Free flowing blood clot or lesion material that is located in the systemic or pulmonary circulation.
 
A peripheral embolic event is an operative, autopsy or clinically documented embolus that produces symptoms from complete or partial obstruction or a peripheral (noncerebral) artery.

Emergency Surgery
	
Emergent Salvage: The patient is undergoing CPR en route to the operating room or prior to anesthesia induction
 
Emergent: All of the following conditions are met:
 
 • Not elective status • Not emergent salvage status • Procedure required before procedure room exit in order to minimize chance of further clinical deterioration • Any surgical procedure on the previously implanted study device (repair, alteration or replacement) or study procedure access site post-implant procedure 
Elective: The patient’s cardiac function has been stable in the days or weeks prior to the operation. The procedure can be deferred without increased risk of compromised cardiac outcome.

Endocarditis
	
An inflammation of the inside lining of the heart chambers and heart valves (endocardium). Endocarditis can involve the heart muscle, heart valves, or lining of the heart.

Enrollment
	
Subject enrollment in this clinical study is established when a subject has signed the informed consent form agreeing to participate in the study and has been deemed eligible for study participation by meeting the study criteria.

Explant
	
Removal of the study device after completion of the implant procedure for any reason.

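### The primary test names no scale for its Kaplan-Meier upper limit, so the 5% level is not secured; separately, enrolling 78 makes 63 likely rather than certain

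*Protocol*

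**What the plan says.** Protocol 13.1 tests 30-day all-cause mortality against a performance goal of 18%. It assumes a true rate of 7.5% or less and states that 63 subjects give at least 80% power at 0.05. Its allowance for losses reads "With a proportion of up to 9 investigational centers utilizing a roll-in subject and with a potential dropout rate of approximately 10" percent, and it concludes that "an enrollment target of 78 subjects will ensure a sample size of 63 is available for analysis".

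Protocol 13.4 and SAP 3.2 give the same rule: a one-sided 95% interval from Kaplan-Meier with Greenwood standard errors, rejecting the null if the upper limit is below 0.18. Neither names a transformation.

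Four other provisions decide who counts:

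- Protocol 13.3 bases the primary endpoint on the As Treated cohort, which requires an incision, and adds that "Roll-In subjects will be analyzed separately".
- Section 19 fixes enrollment before any procedure: "Subject enrollment in this clinical study is established when a subject has signed the informed consent form agreeing to participate", together with meeting the study criteria. Section 8.7.1 says that enrolled subjects who "do not have the study procedure (incision) occur will be exited from the study immediately".
- Section 8.9 says: "A study subject that has been withdrawn from the study will not be replaced".
- SAP 3.5 limits endpoint analyses to patients with the required data and allows no imputation.

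**The concern.** This is the only hypothesis test in a single-arm safety study. Greenwood's formula gives a standard error, but the upper limit also depends on the scale to which that error is applied. With few deaths the scales disagree by a whole death. If the scale is chosen after the data are seen, a result of exactly 7 deaths in 63 can be called a success or a failure.

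The attrition sentence has a related weakness. It promises 63, yet its own planning values taken at their maximum leave slightly fewer. The stated power also depends closely on the exact number analysed.

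**Working it through.** **Inputs.** Performance goal 0.18, true rate 0.075, one-sided level 0.05, 63 analysed, 78 enrolled, up to 9 roll-ins and about 10% dropout (Protocol 13.1). The rule is an upper limit below 0.18 (Protocol 13.4, SAP 3.2).

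**Step 1: reproduce 63.** Use an exact one-sided binomial test and let c be the largest count with P(X ≤ c | n, 0.18) ≤ 0.05. At n = 63, c = 6, type I error is 4.87%, and power is P(X ≤ 6 | 63, 0.075) = 80.8%. This is the smallest n meeting both targets, so the plan's figure reproduces.

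**Step 2: apply the planned limit on each scale at n = 63.** Without censoring, Kaplan-Meier mortality is d/n and the Greenwood error is √(p(1−p)/n). For d = 7, p = 0.1111 and the error is 0.0396. The untransformed limit is 0.1111 + 1.645 × 0.0396 = 0.176, which passes. The log-log limit for the same data is 0.197, which fails. For d = 6 the log-log limit is 0.178, which passes.

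| Scale at n = 63 | Deaths allowed | Type I error | Power at 7.5% |
|---|---|---|---|
| Untransformed, log | 7 | 9.9% | 90.2% |
| Log-log, logit, arcsine, exact | 6 | 4.87% | 80.8% |

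**Step 3: other sizes, no censoring.**

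| n | Untransformed: deaths / error / power | Log-log or exact: deaths / error / power |
|---|---|---|
| 61 | 6 / 6.05% / 82.9% | 5 / 2.6% / 69.3% |
| 62 | 7 / 10.9% / 90.9% | 5 / 2.3% / 68.0% |
| 63 | 7 / 9.9% / 90.2% | 6 / 4.9% / 80.8% |
| 64 | 7 / 9.0% / 89.5% | 6 / 4.4% / 79.8% |
| 69 | 8 / 10.6% / 92.8% | 6 / 2.5% / 74.1% |
| 70 | 8 / 9.6% / 92.2% | 7 / 4.9% / 84.7% |
| 75 | 8 / 6.0% / 89.2% | 7 / 2.9% / 80.1% |
| 78 | 9 / 8.5% / 93.4% | 8 / 4.5% / 87.1% |

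The untransformed limit exceeds 5% at every n from 61 to 78. Logit reaches about 5.5% (n = 69) and arcsine 8.2% (n = 65). Log-log and exact allow the same number of deaths at each n in this range and never exceed 4.92%.

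**Step 4: attrition.** (78 − 9) × 0.90 = 62.1, or 78 × 0.90 − 9 = 61.2. With 9 roll-ins, 63 survives if at most 6 of 69 are lost (8.7%). If each of the 69 has a 10% chance of loss, the probability of that is 45.8%. With 8 roll-ins, (78 − 8) × 0.90 = 63.0. The target of 78 is close to 63 × 1.10 + 9 = 78.3; dividing by 0.90 gives 63/0.90 + 9 = 79 or (63 + 9)/0.90 = 80.

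**Step 5: cost of the shortfall alone.** The smooth approximation is Φ[(0.105√n − 1.645√(0.18 × 0.82)) / √(0.075 × 0.925)]. It gives 77.8% at 63, 77.0% at 62 and 76.2% at 61.

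**Step 6: timing of loss.** Simulations used 69 non-roll-ins, each with a 10% chance of loss, and deaths and later losses uniform over days 0 to 30. The log-log limit gave power of 74.3% with all losses before incision and 77.4% with all losses after incision and censored. The untransformed limit gave type I error of 7.5% to 8.6% across the timing scenarios.

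**The case against.** On attrition the opposing case is strong. Nine roll-ins is a ceiling, since Protocol 6 only allows one per inexperienced center, and 8.7% fits within approximately 10%. The documents do not say that dropout happens before incision. Section 8.10 lists the subject who never has the procedure separately from withdrawal and loss to follow-up, and the no-replacement sentence speaks of withdrawn subjects. If losses come later and are censored, all 69 remain. All of this stands.

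On the limit, four forms deliver the claimed 63, and power at 63 is at least 80% on every form examined; only the level fails, for untransformed and log. SAP 3.1 also names Clopper-Pearson. However, it does so for binary variables and assigns time-to-event variables to Kaplan-Meier, so the primary limit stays unspecified. The SAP's citation of a software manual does not fix the scale either. The analysis-software sections show no text in the public copies; if withheld text names the scale, the main point is answered.

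A reader might infer that the trial is undersized, or that lost patients push power down to 68%. The documents do not support either. The figure of 63 is correct for an exact-type test, and the drop at 61 and 62 is mostly a step from 6 to 5 allowed deaths.

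**Conclusion.** The main point holds: the stated 0.05 level is not secured until the scale is named. At 63 the choice moves type I error between 4.87% and 9.9%; over 61 to 70 an untransformed limit runs from about 6% to 10.9%. These are binomial calculations without censoring before day 30.

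The attrition point is minor. The word *ensure* is too strong by 1 to 2 subjects, and only with 9 roll-ins and a full 10% lost before incision.

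It would go too far to say that 80% power and a 5% level cannot both be met at the sizes 78 can yield. With the log-log or exact limit both are met at 63, at 70 to 75, and at 77 and 78; the larger sizes need fewer roll-ins. Power is below 80% at 61, 62 and 64 to 69. These figures apply at the 7.5% boundary: at a true 6%, exact power is 84.2% at 61 and 83.3% at 62.

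One matter remains open. SAP 3.5 could be read as excluding subjects lost before day 30, while Kaplan-Meier would censor them. On the first reading, later losses also reduce the number analysed.

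**What to change.** 1. In Protocol 13.4 and SAP 3.2, specify the log-log Greenwood upper limit. If there are no deaths the Greenwood error is zero, so specify the one-sided 95% Clopper-Pearson limit for that case. State that As Treated subjects lost before day 30 are censored, and reconcile SAP 3.5 with this.
2. In Protocol 13.1, replace the guarantee with an expectation: about 61 to 62 As Treated non-roll-in subjects with 9 roll-ins and 10% loss before incision, and more with fewer roll-ins or later losses. State the base and timing of dropout.
3. In Protocol 13.1, restate power at a true 7.5% for the log-log or exact limit without censoring: 69.3% at 61, 68.0% at 62, 80.8% at 63, 79.8% falling to 74.1% over 64 to 69, and 84.7% falling to 80.1% over 70 to 75.

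The cost is a few sentences, a less favourable stated power, and 6 rather than 7 deaths allowed at 63 compared with an untransformed limit. No extra patients are needed.
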